# **11 TRIAL ASSESSMENTS**

The following trial assessments will be performed at the timing indicated in the Schedule of Events table on page 13. Below is a detailed description of what each assessment entails.

## 11.1 Demographic and background assessments

- Written informed consent
- Demographic data: Date of birth, ethnic group, sex
- Medical history, incl. treatment history and current medication
- Chest X-ray (X-ray images performed at non-study facilities may be accepted, if there is reasonable certainty that the patients ID is correct, and if they are not older than 2 weeks)
- Method of birth control, both for male and female subjects.

#### 11.2 Efficacy assessments

The assessments of efficacy will be done at multiple fixed time-points during treatment and follow-up phase as follows:

#### Spot sputum

- Method: Participants will be shown images of what good quality sputum samples should look like, which reportedly has led to better sample quality and higher detection rates of MTB.
- Before producing a sample, participants should first rinse their mouth with clean water. Then, they should deeply inhale three times and cough deeply to produce a good quality sample, trying to avoid saliva and nasal secretions. 1 sample is collected at screening visit (SCR), 3 samples are collected per experimental treatment phase visit and two samples during follow-up phase at each visit.
- From two spot sputum samples at visits WK00 to WK16, cultures will be done in MGIT liquid media. At WK00, WK08 and WK12, LJ solid media cultures will be performed from two samples as well. Additionally, the MBLA, a novel assay to measure mycobacterial load by quantifying 16S rRNA from sputum samples, will be performed on stored aliquots of sputum samples collected at all study visits; and evaluation of LAM concentration will be performed as experimental determination of bacterial load, both depending on test availability.
- During follow-up phase at visits FU 1-4 the two spot sputum samples will be processed for mycobacterial culture MGIT liquid culture, Ziehl-Neelsen stained sputum smear and for LJ on solid media.
- If the volume of sputum sampled is too small for all tests to be done, culture in MGIT liquid media will be prioritised as these data are required for evaluation of the primary study end-point.

- The infecting isolate will be stored from a positive culture of a sample obtained prior to treatment start, from visits during experimental treatment, and from every positive culture obtained at or after visit WK08, for assessments of MICs and typing by molecular bacteriology, to be specified in the Laboratory Manual.
- The methodology will be described in detail in the Laboratory Manual, which will be supplied to the trial sites before study start.

# 11.3 Safety assessments

#### Electrocardiography

ECGs are to be performed after a period of at least 10 minutes of recumbent (lying down) rest; and before any other procedures are done.

At visit WK00, a 12-lead ECGs will be performed in triplicate. At all other visits, a single ECG will suffice, unless the following is observed:

If a QTcF of >480ms, or a prolongation over baseline of >50ms is seen in a single on-treatment or unscheduled ECG, two more ECGs should be registered, to obtain an average QTcF measurement that will be more precise than the estimate from a single ECG.

12-lead ECG analysis will be performed. The following ECG variables will be assessed for safety endpoint: Heart rate, PQ interval, QRS, QT, and QT corrected for heart rate using Fridericia correction (QTcF), morphological abnormalities.

- Method: Single ECGs will be recorded for at least 10 seconds pre-dose at 50mm/second or greater. Timing and registration technique for ECGs will be standardized for all participants. Patients should be lying down (recumbent) for at least 10 minutes prior to each 12-lead ECG evaluation. For each participant, the ECG should be collected at around the same time of day, preferably within 2 hours before dosing.
- $\circ~$  ECGs will be analysed immediately by site investigators to ascertain patient safety.

#### Screening/Safety laboratory tests

Samples for laboratory tests are to be taken before the day's dose of study treatment is administered.

- Urine:
  - Urine drug screening by a rapid test for opiates, amphetamines, cannabinoids, cocaine, benzodiazepines and barbiturates.
  - Urinalysis\*: Dipstick for pH, protein, glucose, ketones, urobilinogen, blood and leukocytes.
  - $\circ$   $\;$   $\;$  Urine microscopy on abnormal dipstick results as per the investigator's decision.

- Blood:
  - Serum pregnancy test, if female of childbearing potential (SCR, WK09 and WK18)
  - $\circ$  HIV test (CD4 count if HIV positive, additionally viral load, if patient is on ARVs, additionally genotypic resistance testing, if viral load is >1,000 copies/µL) and patient would have to be switched to a non-dolutegravir ART regimen after end of study (SCR)
  - Haematology\*: Complete blood count with differential and platelets
  - Biochemistry\*: ALT, AST, gamma-glutamyl transferase (yGT), alkaline Phosphatase (aP), lipase, direct and total bilirubin, albumin, serum creatinine, electrolytes (Na+, K+, Serum Calcium, Magnesium, Cl-, PO43-), random glucose
  - Coagulation: aPTT, PT, INR

\*performed during safety laboratory assessment, complete list of tests done during screening only

#### **Physical examination**

Details about the conduct of physical examination will be laid out in the Manual of Procedures (MOP)

- Weight (kg)/height (m)
- Physical examination
- Additionally, the Hunter criteria for early detection of serotonin syndrome will be assessed:
  - Spontaneous clonus
  - Inducible clonus
  - Ocular clonus
  - o Tremor
  - Hyperreflexia
  - o Agitation
  - Diaphoresis
  - Hyperthermia above 38ºC

Serotonin syndrome is diagnosed according to the following decision rule, which will prompt stopping a subject from receiving study drug if fulfilled. The Hunter Serotonin Toxicity Criteria are fulfilled if any of the following is fulfilled:

- Spontaneous clonus
- Inducible clonus PLUS agitation or diaphoresis
- Ocular clonus PLUS agitation or diaphoresis

- o Tremor PLUS hyperreflexia
- Hypertonia PLUS temperature above 38°C PLUS ocular clonus or inducible clonus

In the case of presence of newly appearing symptoms "inducible clonus", "ocular clonus", or "tremor", which would not fulfil Hunter criteria on their own, close observation of the participant (ideally daily) is warranted while continuing on medication, and the sponsor medical expert should be notified.

- Vital signs (temperature (degrees Celsius), blood pressure (systolic and diastolic, in mmHg), pulse (bpm), pulse oxymetry, and respiratory rate (breaths/minute)). Measurements for blood pressure and pulse rate will be performed in the supine position after at least 10 minutes rest using an oscillometric method. As far as possible, measurement will always be performed on the same arm.
- On visits WK00 and WK02, additional blood pressure measurements will be performed: WK00: after 1h, 2h and 3h (± 10 mins) after IMP is taken; WK02: 1h, 2h, 3h, 4h, 6h (± 10 mins) after intake of IMP

#### Detailed neurological examination

The detailed neurological examination will be laid out in the Manual of Procedures (MOP)

- Neurological examination including the following assessments:
  - Cranial nerves
    - Test both pupillary responses to light
    - Eye movements in all directions
    - Palatal movement
    - Tongue movement
  - Reflexes: Biceps, Achilles' and patellar tendon reflexes bilaterally
  - o Sensory: Vibration sensitivity, pin prick, light touch

#### Vision testing

The vision testing will be laid out in the Manual of Procedures (MOP)

- Visual acuity testing according to Snellen
- Vision testing for colour deficiencies according to Ishihara

# Compliance assessment for food and beverage restrictions (at SCR and during experimental treatment WK00 – WK16)

The investigator will assess the risk to the participant by questioning about their usual diet and drinking habits, and about their understanding of which beverages they usually take are not permitted in the study.

The investigator will have to come to the conclusion at screening that the participant will likely comply, for a participant to be eligible to study participation.

#### 11.4 Assessments when Recurrence is Suspected

During follow-up, patients who are experiencing complaints, or have laboratory events suggesting a recurrence of disease, will be evaluated in a standardized manner that has been described for the TBTC study 31 [58].

Triggers for the assessment will be the following events:

- A positive culture confirmed as M. tuberculosis from a sputum specimen collected at or after the WK16 visit
- Worsening signs and/or symptoms consistent with tuberculosis at or after WK16
- The site investigator is considering an extension of tuberculosis therapy beyond 16 weeks

The following procedures shall be conducted:

- Assessment of symptoms
- Review interval medical history
- Weight, vital signs and physical examination
- Obtain 3 sputum specimens for smear and MGIT plus LJ culture, 2 specimens at least 4h apart. If M. tuberculosis is isolated, the isolate is to be stored frozen.
- Chest radiograph
- Review participant's contact information, and update if indicated
- Contact sponsor medical expert to review procedures, results and decide on management

The outcome of this assessment will be twofold:

- to define whether the patient will have met the endpoint of "relapse", conditional on a matching of baseline and recurrence isolate, if available;
- to transfer the patient to the government TB treatment programme to receive treatment for recurrent disease

#### 11.5 Pharmacokinetic assessments

The exact time of drug administration will be recorded on the day of PK sampling and will be defined as 0h for the following PK sampling procedures. The timing of drug administration on the two preceding days will also be recorded.

#### Delpazolid

All patients will undergo intensive PK sampling at Day 14 (WK02) visit. A sample will be drawn within 1h before administration of the DZD morning dose (0 h).

The DZD morning dose will be administered with a standardized meal. Blood draws thereafter will be performed at 1, 2, 4, 8, 12 (± 10 mins) and 24 hours (± 30 mins) after DZD morning dose. The exact time of meal and DZD administration at the day of PK sampling will be recorded. Standardized food and fluid intake will be monitored and noted throughout the PK days.

Procedures for sample connection, storage and transportation will be described in the Laboratory Manual. Assaying of DZD, BDQ and DLM plus main metabolites, and MXF will be conducted centrally at the Department of Pharmacy, Radboudumc, the Netherlands, with validated LC-MS/MS methods.

Pharmacokinetic parameters will be assessed using non-compartmental techniques and nonlinear mixed effects methodology. The latter will be utilized to develop a population PK model describing DZD, which will be linked to safety and efficacy parameters. Secondary PK parameters to be reported are listed in section 9.2.3.

#### 11.6 Additional biomarker assessments

The main evaluation of treatment response biomarkers in this study focus on sputum microbiology (via serial MGIT and LJ cultures); and the experimental assessments for LAM, and the MBLA). Collection and appropriate storage of plasma and whole blood samples will permit exploratory evaluation of host immunological and transcriptomic biomarkers as sub-studies. In addition, a sample for pharmacogenomics analyses will be stored at screening (see section 20.3.3). Sampling for these sub-studies will be conditional on participant approval to storage, and genetic testing.

# **12 STUDY TREATMENT**

# **12.1** Study drug regimens

The study will recruit into the following arms:

Arm 1 (D 0 ): BDM	(bedaquiline, delamanid, moxifloxacin)
Arm 2 (D 400 ): BDM + DZD	(bedaquiline, delamanid, moxifloxacin, delpazolid 400 mg OD)
Arm 3 (D 800 ): BDM + DZD	(bedaquiline, delamanid, moxifloxacin, delpazolid 800 mg OD)
Arm 4 (D 1200 ): BDM + DZD	(bedaquiline, delamanid, moxifloxacin, delpazolid 1200 mg OD)
Arm 5 (D 800-BD ): BDM + DZD	(bedaquiline, delamanid, moxifloxacin, delpazolid 800 mg BID)

BDQ, DLM, MXF are approved drugs. Product Information Leaflets for these drugs will be provided to investigators.

DZD is not an approved drug. It will be manufactured and tested according to Good Manufacturing Practice (GMP) requirements. The Sponsor will provide Ethical Review Boards and site investigators with a set of documents, as required by the local regulatory authority, that provides information on the manufacture and quality control of the raw substance and the medicinal product; Certificates of Analysis (CoA) of the batches to be used; and an Investigational Brochure (IB) that summarizes preclinical and clinical data with respect to DZD.

# 12.2 Study drug dosage and administration

The experimental and control treatment as described above will be administered daily for 16 weeks (see Table 1. Daily Dosing of Study Medication), together with food.

- Bedaquiline: will be dosed as per the licensed dose: 400 mg orally once daily for the first 14 days, then 200 mg three times a week.
- Delamanid: will be dosed as per the licensed dose: 200 mg orally in two daily doses of 100 mg.
- Moxifloxacin: will be dosed as per the licensed dose: 400 mg orally once daily
- Delpazolid not licensed:
  - Dose: will be according to randomization to dosing arm:
    - Arm 1: 15 participants will receive 0 mg of DZD
    - Arm 2: 15 participants will receive 400 mg DZD orally once daily
    - Arm 3: 15 participants will receive 800 mg DZD orally once daily
    - Arm 4: 15 participants will receive 1200 mg DZD orally once daily
    - Arm 5: 15 participants will receive 800 mg DZD orally twice daily

The daily dose of study drug for participants will be dependent on the subjects' experimental arm as shown in the following table:

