#### Table 1. Daily Dosing of Study Medication

	Bedaquiline (Sirturo®)	Delamanid 50 mg tablet	Moxifloxacin 400 mg tablet	Delpazolid 400 mg tablet
	100 mg tablet			
Arm 1 (D0): BDM	Day 01-14: 4 tablets to be taken orally once	Day 01-112: 2 tablets to be taken orally 2	Day 01-112: 1 tablet to be taken orally once per day	
	per day in the mornings Day 15-112:	times per day (mornings and evenings)	in the mornings	
	2 tablets to be taken orally 3 times per week in the mornings			
Arm 2 (D400):	Day 01-14:	Day 01-112:	Day 01-112:	Day 01-112:
0014 070	4 tablets to be	2 tablets to be	1 tablet to be taken	1 tablet to be taken
BDIM-DZD	taken orally once	taken orally 2	orally once per day	orally once per day
	mornings	(mornings and evenings)	in the mornings	in the mornings
	Day 15-112:			
	2 tablets to be			
	ner week in the			
	mornings			
Arm 3 (D 800-OD ):	Day 01-14:	Day 01-112:	Day 01-112:	Day 01-112:
	4 tablets to be	2 tablets to be	1 tablet to be taken	2 tablets to be
BDM-DZD	taken orally once	taken orally 2	orally once per day	taken orally once
	per day in the mornings	times per day (mornings and evenings)	in the mornings	per day in the mornings
	Day 15-112:			
	2 tablets to be			
	taken orally 3 times			
	per week in the			
	mornings	D. 01 112	D. 01 112	D. 01 112
Arm 4 (D1200):	Day 01-14: A tablets to be	Day 01-112: 2 tablets to be	Day 01-112: 1 tablet to be taken	Day 01-112: 2 tablets to be
	taken orally once	taken orally 2	orally once per day	taken orally once
	per day in the	times per day	in the mornings	per day in the
	mornings	(mornings and evenings)		mornings
	Day 15-112:			
	2 tablets to be			
	taken orally 3 times			

	per week in the mornings			
Arm 5 (D800-BD):	Day 01-14: 4 tablets to be	Day 01-112: 2 tablets to be	Day 01-112: 1 tablet to be taken	Day 01-112: 2 tablets to be
BDM-DZD	taken orally once per day in the mornings Day 15-112: 2 tablet to be taken orally 3 times per week in the mornings	taken orally 2 times per day (mornings and evenings)	orally once per day in the mornings	taken orally 2 times per day (mornings and evenings)

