# 12.3 Study drug management

A Study Drug Management Plan (DMP) will describe all aspects of drug management in this study, including details on packaging, labelling, storage conditions, distribution, drug-dispensing, drug accountability and other drug-related procedures. A team of pharmacists, including a pharmacist at each study site, will be responsible for study drug management.

The Sponsor will supply the study drugs to allow completion of this study including spare drugs.

The overall intent of the labelling of the study drugs is to ensure the protection of the trial participants, to ensure traceability and identification of the drugs and trial at all times, to facilitate the proper use of the drugs, and to comply with national and international regulations on investigational drugs. The study drugs will be labelled for the study according to *The Rules Governing Medicinal Products in the European Union,* Annex 13 of GMP, and to national labelling requirements of the study sites.

All study medication must be kept in secure cabinets or rooms with access restricted to designated study personnel. Medication will be stored at appropriate conditions at designated temperatures,

protected from light and moisture. A temperature monitoring system will be in place to monitor appropriate storage conditions and record possible deviations.

The dispensing of study drugs for individual patients will be performed and recorded as described in the DMP. Dispensing at each site will be supervised by a pharmacist. Dispensing will only be performed by licensed and trained study personnel.

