4.1. Overview

This will be an open label Phase IIb dose-finding, randomized, controlled study with a duration of 16 weeks of experimental therapy of DZD – Bedaquiline/Delamanid/Moxifloxacin (BDM) in adult participants with newly diagnosed, smear positive, uncomplicated, drug sensitive pulmonary tuberculosis (TB) to evaluate the safety, efficacy, tolerability, pharmacokinetics and exposure/response-relationship of different doses of delpazolid in combination with bedaquiline, delamanid and moxifloxacin.

Participants will be randomized to one of five arms containing BDM with different doses of DZD:

- Arm 1 (D0): 15 participants will receive 0 mg of DZD.
- Arm 2 (D400): 15 participants will receive 400 mg DZD orally once daily.
- Arm 3 (D800-OD): 15 participants will receive 800 mg DZD orally once daily.
- Arm 4 (D1200): 15 participants will receive 1200 mg DZD orally once daily.
- Arm 5 (D800-BD): 15 participants will receive 800 mg DZD orally twice daily.

Participants will visit the study clinic on a weekly basis for sputum collection, safety monitoring and receipt of study medication. After the completion of 16 weeks of experimental treatment, participants in the experimental arms, who did not achieve two successive negative liquid media cultures with the first at or before WK08, with no positives to follow by the week 16 visit, will be referred to their local health care facility to complete their course of anti-TB treatment according to the national TB program.

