8.2. Data Management

A NONMEM dataset will be generated through reproducible scripting in R. The raw PK data will be supplied from the Clinical Pharmacology lab, Radboudumc, in prespecified format (template to be agreed upon between lab and pharmacometrician before start of analysis). Patient characteristics and information about doses and sampling will be extracted from the main database provided from the responsible CRO (Tecro). Actual dosing and sampling dates and times will be used.

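### Protocol Table 1 gives Arm 4 (D1200) two 400 mg delpazolid tablets once daily, which is 800 mg; the cell should read three tablets

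*Protocol*

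**What the plan says.** The intended Arm 4 dose is stated consistently in the text. Protocol 12.1 lists the arm as "bedaquiline, delamanid, moxifloxacin, delpazolid 1200 mg OD". Protocol 12.2 says "Arm 4: 15 participants will receive 1200 mg DZD orally once daily". The synopsis gives the same dose under both study design and dosage, and SAP 4.1 repeats it: "Arm 4 (D1200): 15 participants will receive 1200 mg DZD orally once daily".

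After its list of arms, Protocol 12.2 says that the daily dose depends on the "experimental arm as shown in the following table". That table is Table 1. Its last column is headed "Delpazolid 400 mg tablet", and Protocol 6.1 describes 400 mg as the tablet strength for this trial. Read across the bedaquiline, delamanid, moxifloxacin and delpazolid columns, the Arm 4 row begins "A tablets to be Day 01-112: 2 tablets to be Day 01-112: 1 tablet to be taken Day 01-112: 2 tablets to be". The delpazolid cell continues with once-daily morning intake.

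Protocol 12.3 places dispensing under a separate plan: "The dispensing of study drugs for individual patients will be performed and recorded as described in the DMP".

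**The concern.** Two 400 mg tablets once a day are 800 mg, not 1200 mg, and the Arm 4 cell is identical to the Arm 3 (D800-OD) cell. Table 1 is the only place in the two documents that converts an arm into a number of tablets. Someone working from the table alone would see a complete, unremarkable instruction for an unlicensed drug.

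If the cell were followed, three things would be at stake.

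- **The design.** Two arms would be on 800 mg once daily and none on 1200 mg. Arm 4 is also the only arm with a single intake above 800 mg (Arm 5 takes 800 mg per intake), so the upper range of Cmax depends on it. Cmax is one of the three exposure metrics in SAP 10.2.
- **Safety information.** In the phase 2a study summarised in Protocol 6.1.4, 1200 mg once daily had the highest adverse drug reaction rate of the delpazolid groups (6/16). Experience at that dose would be missing while being reported as present.
- **The population PK model.** Under SAP 8.2, "information about doses and sampling will be extracted from the main database". SAP 8.3.1 explores non-linear relations between dose and bioavailability, and Table 2 of SAP 8.3.3 lists dose as a covariate on bioavailability. If the database held the assigned 1200 mg while 800 mg was taken, the model would see a dose effect that does not exist.

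**Working it through.** **Inputs.** Tablet strength is 400 mg (Table 1 heading; Protocol 6.1). Stated doses come from Protocol 12.2, tablet counts and the 112-day period from Table 1, and 15 participants per arm from Protocol 12.2.

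**Formula.** Daily dose = tablets per intake × intakes per day × 400 mg.

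| Arm | Table 1 | Computed | Stated | Match |
|---|---|---|---|---|
| 2 (D400) | 1 × 1 | 400 mg | 400 mg | yes |
| 3 (D800-OD) | 2 × 1 | 800 mg | 800 mg | yes |
| 4 (D1200) | 2 × 1 | 800 mg | 1200 mg | **no** |
| 5 (D800-BD) | 2 × 2 | 1600 mg | 1600 mg | yes |
| 4, corrected | 3 × 1 | 1200 mg | 1200 mg | yes |

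The companion drugs also reproduce: bedaquiline 4 × 100 = 400 mg, then 2 × 100 = 200 mg; delamanid 2 × 2 × 50 = 200 mg per day; moxifloxacin 1 × 400 = 400 mg. The Arm 4 delpazolid cell is the only one that fails, and three is the only tablet count that gives 1200 mg in one intake.

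**Size if the cell were followed.**

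- Dose: 800/1200 = 0.667, a shortfall of 33%.
- Tablets per participant: 2 × 112 = 224 against 3 × 112 = 336.
- Tablets for the arm, assuming 15 participants and full adherence: 224 × 15 = 3,360 against 336 × 15 = 5,040.

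**Dose spread (illustration only; a linear slope on nominal dose with equal arms is not a planned analysis).** The sum of squared deviations of {0, 400, 800, 1200, 1600} about 800 is 1,600,000. For {0, 400, 800, 800, 1600} about 720 it is 1,408,000. The ratio is 0.88, so the slope's standard error would rise by a factor of √(1/0.88) = 1.066, or 6.6%.

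**Population PK.** If 1200 mg were recorded and 800 mg taken, apparent relative bioavailability in Arm 4 would be 800/1200 = 0.67, a spurious fall of 33%. That exceeds the 20% difference in exposure that SAP 8.3.3 treats as clinically relevant.

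**The case against.** The strongest objection is that the digit may be a misread. The row is poorly extracted: the bedaquiline count in the same row appears as A instead of 4, the day-range headings seem to be duplicated in garbled form just above it, the regimen label is missing and the row crosses a page break. This stands as a reason to look at the original page before anything else. The delpazolid cell does form a complete and legible instruction, but a misread 3 cannot be excluded.

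Second, the intent is unambiguous. The row is labelled D1200, the 1200 mg dose stands immediately before the table, and pharmacists dispense under the Drug Management Plan. This also stands: there is no evidence that anyone was underdosed. It does not remove the conflict, because 12.2 itself sends the reader to the table.

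Third, the modelling harm needs several failures in a row: sites following the table, the database holding 1200 mg, and nobody noticing despite individual dispensing records (Protocol 12.3.2), pill counts at every visit and observed intake at study visits (Protocol 12.5). SAP 8.3.3 also requires checks of influential individuals and of plausibility before a covariate is kept. These safeguards make the outcome unlikely. The plausibility check is a weak one here, though, because lower bioavailability at the highest single dose could pass as saturable absorption. The effect on the primary exposure-response model would be modest, since SAP 10.2 uses individual PK metrics.

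Finally, timing. Recruitment was planned to end in Q1 2022 and the SAP is dated February 2023. If recruitment ran to plan, which the documents do not show, correcting the cell would come too late to affect dosing. The records check would then be the part that matters.

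**Conclusion.** The point holds. As it reads, Table 1 doses Arm 4 at 800 mg per day, two thirds of the 1200 mg stated everywhere else, and makes it identical to Arm 3. The error is confined to one cell and the right value is not in doubt.

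The conclusion assumes that the extracted cell matches the original page. The consequences for design, safety and population PK are conditional on the cell having been followed, which the documents neither show nor rule out. Because this is a dosing instruction, it should be corrected or shown to be a misread, and not left as an assumed typing slip.

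**What to change.** 1. Check the Arm 4 row of Table 1 on the original page.
2. If the cell does say two, change it to three tablets by mouth once a day in the morning, days 1 to 112.
3. Confirm that the Drug Management Plan, labels and accountability forms give three tablets for Arm 4.
4. Before the population PK, by-arm and adherence analyses, reconcile Arm 4 dispensing and pill-count records with the doses in the database. Report any participant whose records show two tablets, and use the dose actually taken in the PK model.

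The cost is one table cell, handled through the amendment process in Protocol 18.7, plus a document check and a records review for 15 participants. If dosing is already complete, step 4 is still worth doing: it documents that Arm 4 received 1200 mg, on which every result for that arm relies.
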